4. Research Plan/Methods

Overview

This project will evaluate the effectiveness of alternative second-line treatment according to patient-level measures routinely recorded in primary care data. We will use CPRD-HES data to develop a model to provide accurate estimates of the long-term incidence of macro- and micro- vascular complications for patients with T2DM in England. The CPRD is an exceptional source of anonymised population-based electronic health records. These primary care records combining both GOLD and Aurum datasets comprise a representative sample of ~20% of the UK population and contain comprehensive high quality data on clinical diagnoses, prescribing, referrals, tests and demographic/lifestyle factors^{9, 30}. Linkage between the primary care records in CPRD and HES is well established for >70% of practices in the CPRD, providing a data set augmented with detailed secondary care diagnostic and procedural records. Our group is experienced in using these data to conduct high quality studies, including of evaluating treatments for T2DM²⁷.

Instrumental variable design

Studies which apply traditional risk adjustment approaches when there is little information on case-severity are liable to provide biased estimates of treatment effectiveness. We therefore propose an IV study design^{1, 2}. A valid IV design can provide accurate estimates of treatment effectiveness even when there are unmeasured differences between the comparison groups^{1, 2}. An IV encourages receipt of the treatment, in this case first-stage treatment intensification, but does not have a direct effect on the outcome, for example HbA1c, except through the treatment prescribed (Fig. 1).

The IV for the prescription of each first-stage treatment intensification regimen is the CCG's prescribing history, which reflects that the choice of second-line treatment may involve the hospital diabetologist, the GP, other health-care professionals, and the patient. We will define 'CCG prescribing history' as the proportion of patients prescribed each first-stage treatment intensification in the CCG for the last complete calendar year prior to the treatment intensification of the patient currently under consideration.

[figure not shown]

Fig. 1. Instrumental variable design.

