We will extract all the required information on prescriptions by extending previous algorithms developed to identify antidiabetic regimens from CPRD, ⁷ to extract all the required information on concomitant medications. A major challenge is that for each drug, the definitions will be required to consistent with those applied to the United States Department of Veterans Affairs (VA) electronic medical record and Medicare Claims databases in building the original RAPIDS model. The study will therefore develop general codes to identify all the anti-diabetic, anti-hypertensives and lipid lowering drugs based on British National Formulary chapter and drug codes. We will use these codes to identify the second-line treatment, and extract the dose and estimated dates of initiation and cessation for each treatment. To provide measures of long-term effectiveness requires that information on all relevant prescriptions is extracted for the maximum follow-up time for each patient.

Outcomes

From the onset of second-line treatment until the maximum duration of follow-up, the study will extract information from the CPRD on biomarkers (HbA1c, HDL, LDL and total cholesterol, triglycerides, SBP, DBP, eGFR, body weight, and BMI). Follow-up for all patients will be censored at the date of death, transfer out of the practice or end of data collection, whichever is earliest. We will report the time to cessation of first-line intensification. From the HES-linked data, we will use ICD10 diagnostic codes as primary or secondary diagnoses, to identify inpatient hospital admissions associated with T2DM including hypoglycaemia, MI, CHF, unstable angina, stroke, ESRD, and lower limb amputation. We will extract information on mortality, including date of death, from linkage to ONS mortality data.

Missing data in the CPRD-HES linked cohort

The main potential issues are missing values for baseline case-mix variables and biomarkers at particular time-points. Drawing on the precedent study we expect <5% of patients will have missing values for baseline variables such as BMI, with the exception of ethnicity (c10%), for which missing data will be minimised by using HES admission data from linked episodes.

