The RAPIDS model predicts levels of intermediate outcomes over time, including HbA1c; BMI; serum highdensity lipoprotein (HDL); low-density lipoprotein (LDL); and total cholesterol; serum triglycerides; SBP; DBP and eGFR (see Figure 4).²⁹ This model estimates probabilities of all-cause death and other clinical events, such as advanced diabetic eye disease, hypoglycaemia, myocardial infarction (MI), unstable angina, stroke, heart failure (HF), lower-extremity amputation (LEA), and ESKD. The inputs required by RAPIDS to estimate such probabilities include a mixture of constant risk factors (sex and ethnicity), and time-updated (over each 90-day quarter) risk factors, such as age, duration of diabetes, treatments prescribed (glucose-lowering agents, statins, and blood pressure-lowering drugs), and histories of CVD and hypoglycaemia.

We will extend the RAPIDS microsimulation model for a T2DM population in England to predict long-term outcomes following the initiation of one of the three second-line antidiabetic therapies of interest. This model will recognise diverse treatment patterns observed in routine clinical practice. We will calibrate predicted values and assess the external validation of RAPIDS when the model is applied to CPRD data.⁵¹ We will compare the predicted outcomes across the alternative second-line treatments over a maximum follow-up of 7.6 years. We will calculate the between-treatment differences in the means of these predictions together with 95% CI. We will report the comparative effectiveness of these alternative second-line treatments on these long-term

outcomes, both overall and stratified by baseline CVD status. We will implement RAPIDS in R 4.3.1.

Outputs

We will provide an individual-level simulation model for T2DM that accurately predicts long-term outcomes according to the risk profile of general populations of people with T2DM in the UK presenting for second-line treatment. We will provide estimates of the comparative effectiveness of the alternative treatments according to long-term outcomes.

[figure not shown]

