The application has benefited from the input of co-applicant [name], a Patient Research Ambassador Initiative member, and member of the NIHR HTA commissioning board, and [name], a patient with T2DM. The PPI representatives felt that the study design and interpretation should be informed by experiences of patients with T2DM, and have supported plans for two workshops which will include PP representatives. The first (design) workshop will inform the way personalisation is defined, and the prioritisation of the different outcome measures, and the second (translation) workshop will focus on interpretation and communication of results.

We will work with the LSHTM media department, and our lay representatives to ensure the findings are accessible to the broader public. The study website will be an important repository of information about the study methods and findings, for both lay and professional audiences. A full and complete account of the research will be made available by open access as a publication in the NIHR HTA Journal. Research papers will be published in peer-reviewed journals.

7.Project/research timetable

Grant Start date: January 2020

6 Months prior	Development of initial study protocols		
to grant start	University ethics application and approval		
to grant otart			
Months 0-9	Application and receipt of CPRD data		
	Data cleaning, testing of provisional drug coding algorithms consistent		
	with GOLD and Aurum CPRD data, and VA data (US)		
	Extraction of HES admissions according to ICD-10 codes		
	Preparation of summary data for discussion at clinical/PPI panel		
Month 6	Clinical/PPI panel to refine subgroup definitions, prioritisation of		
	outcomes (Design workshop)		
Month 9	Advisory Group Meeting		
	Finalisation of study protocols and analysis plans		
	Approval of final amendments to ethics applications		
Months 9-12	Application of final coding algorithms to full CPRD-HES linked data		
	Submission of paper to Health Economics Study Group on IV design		
	Final study protocols, study design publications in open access journals		
Months 13-18	Inequalities analysis (obj 1)		
	Submit paper I		
Month 12	Interim report to NIHR		
Months 13-28	comparative effectiveness analysis (obj 2)		
	submit paper II		
Month 24	Interim report to NIHR		
Month 27	Advisory Group meeting		
Month 29-36	Heterogeneity analysis (obj 3)		
	Submit paper III		
Month 36	Interim report to NIHR		
Month 37-44	MLTC analysis (obj 4)		
	Submit paper IV		

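### Lower limb amputation is identified in HES by ICD-10 diagnosis codes although it is an operation, so new amputations can be missed or misdated and earlier limb loss can be counted as new (objective 5 only)

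*Protocol*

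**What the plan says.** The general Outcomes paragraph of Protocol section 4 gives one rule for events taken from HES: "we will use ICD10 diagnostic codes as primary or secondary diagnoses, to identify inpatient hospital admissions associated with T2DM". The events it covers are listed directly after, "including hypoglycaemia, MI, CHF, unstable angina, stroke, ESRD, and lower limb amputation". No separate rule follows for amputation.

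The timetable (section 7, months 0-9) describes the same step as "Extraction of HES admissions according to ICD-10 codes".

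The Overview at the start of section 4 describes what HES linkage adds: "providing a data set augmented with detailed secondary care diagnostic and procedural records". The Protocol therefore treats diagnoses and procedures as two kinds of record and says that both are available.

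Amputation is used under Objective 5, where the clinical events predicted by RAPIDS include "heart failure (HF), lower-extremity amputation (LEA), and ESKD". The role of the UK data there is stated as: "We will calibrate predicted values and assess the external validation of RAPIDS when the model is applied to CPRD data".

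**The concern.** A diagnosis classification records conditions and states. It can show why a limb was removed, or that a limb is absent, but it does not record the operation or its date. For most of the listed events, such as myocardial infarction or stroke, the diagnosis is the event and the rule fits. For amputation the rule captures something adjacent to the event.

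Two kinds of error can follow. An admission for a new amputation is found only if a diagnosis code on the list happens to be recorded, and if that code first appears at a later admission the date is wrong. In the other direction, because secondary diagnoses count, limb loss that predates second-line treatment and is noted at an unrelated admission can enter as a new event.

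At stake is the observed UK amputation experience in objective 5. If it is mis-measured, calibration can move the predicted rate towards a wrong target, and external validation against the same variable would not reveal the problem.

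**Working it through.** The Protocol states no figure for amputation, so there is none to reproduce. The check is a comparison of places in the text, followed by an illustration on assumed values.

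**Comparison of the text**

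1. *Type of code.* The general Outcomes paragraph names diagnostic codes, in primary or secondary position. The timetable names ICD-10. No place names a procedure field or an operation date for any outcome.
2. *Available data.* The Overview says procedural records come with the linkage, so the suitable source is in hand and has no stated use.
3. *New versus old limb loss.* No rule separates them. The patient-level covariates are taken from the year before second-line treatment. The comorbidity examples there are CVD, CHF and CKD. The list is open, and amputation is not named.
4. *What the model needs.* Objective 5 updates its time-varying risk factors every 90 days, and the Fig. 4 legend describes transitions over time periods. Calibrating or validating such a model needs new events with usable dates. A code for an absent limb supplies neither reliably.
5. *Reach.* Amputation is not among the objective 2 outcomes (HbA1c, BMI, SBP, eGFR, and the kidney, cardiovascular and mortality events). It is not the outcome of objective 3 or 4, both of which use HbA1c. Only objective 5 is affected.

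**Why no size can be given**

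Every rate below is an assumption; only the cohort size and the follow-up limit come from the Protocol.

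- Long-term cohort: 38,000 + 29,000 + 8,000 = 75,000.
- Assumed: 2 new amputations per 1,000 person-years; 30-60% of them carrying a qualifying diagnosis code; 0.5-1% of the cohort with earlier limb loss; 25% admitted per year; limb status coded in half of those admissions.

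Year 1:

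- New amputations: 0.002 × 75,000 = 150; found: 45 to 90.
- Old limb loss counted as new: 75,000 × (0.005 to 0.01) × 0.25 × 0.5 = about 47 to 94.
- Share of counted events that are new amputations: 45/(45 + 94) = 32% to 90/(90 + 47) = 66%.

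Full 7.6 years for everyone, no attrition, each old case counted once:

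- New amputations: 150 × 7.6 = 1,140; found: 342 to 684.
- Chance that an old case is flagged at least once: 1 − (1 − 0.125)^7.6 = 0.638. Old cases counted: 375 × 0.638 = 239 to 750 × 0.638 = 478.
- Share: 342/(342 + 478) = 42% to 684/(684 + 239) = 74%.

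The share runs from 32% to 74% depending on the window and on rates the Protocol does not supply. This shows how the two errors combine. It does not estimate their size in this study.

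**The case against.** The strongest reply is that this is one summary sentence covering seven outcomes and does not say that diagnosis codes are the only source. The timetable plans final analysis plans and final coding algorithms, and outcome code lists commonly sit in a document not shown here. That would answer a complaint that the code list is absent. It does not answer this one, because the Protocol fixes the type of code as diagnostic, and a list written within that rule would contain no procedure codes.

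A second reply is that the limits of diagnosis coding are general knowledge and not stated in the Protocol. This is true of the detail. The basic distinction, however, is the Protocol's own, since the Overview separates diagnostic from procedural records.

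A third reply is that counting old limb loss requires absent-limb codes on the list and no exclusion of earlier cases. The Protocol states neither, and the covariate list is said to cover what RAPIDS-UK needs. This stands as a reason to say that the error can happen, not that it will.

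The narrow consequences also stand. Objective 5 does not say which predictions are recalibrated, and its treatment comparison is a difference in mean model predictions. Amputation counts from HES reach that comparison only through whatever calibration is done.

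**Conclusion.** The point holds as a wrong measurement rule for one outcome, and it should be corrected. As written, new lower limb amputations can be missed or misdated and limb loss before baseline can be counted as new. This touches the observed UK amputation rate and dates used for calibration and external validation in objective 5. The HbA1c primary outcome, the objective 2 secondary outcomes and objectives 3 and 4 are unaffected.

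Three stronger conclusions might be inferred, and the Protocol supports none of them.

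- *That new amputations are missed as a rule.* Some will carry a qualifying diagnosis code at the same or a later admission, and the share is unknown.
- *That the comparison of SU, DPP4i and SGLT2i for amputation is biased.* The familiar result, observed risk difference = (sensitivity + specificity − 1) × true difference, applies to directly observed risks with equal misclassification across drugs. Objective 5 compares model predictions, and the Protocol does not show how an error in HES counts would carry through to them.
- *That the size of the error is known.* The percentages in the illustration rest on assumed rates and change with the length of follow-up.

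The conclusion rests on the stated code type and on the Protocol's distinction between diagnostic and procedural records. It does not rest on any assumed rate.

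**What to change.** In the general Outcomes paragraph of section 4, take lower limb amputation out of the diagnosis-code rule and give it its own:

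- identify incident amputation from the HES procedure fields, with the operation date as the event date;
- use diagnosis codes for an absent limb only to identify amputation before baseline.

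In section 7, change the months 0-9 extraction line to read 'ICD-10 and procedure codes'.

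The cost is one extra code list applied to records the Protocol says are already linked. No new patients or data collection are needed.

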Previous research has raised several hypotheses about risk factors that could modify the relative effectiveness of alternative second-line drugs. First, SGLT2is may be more effective than SUs or DPP4i in reducing subsequent events in patients with pre-existing CVD. Second, for patients with chronic kidney disease (CKD), SGLT2is may be relatively effective in reducing disease progression²⁶. Third, for patients with MLTCs the relative effectiveness of the alternative drug classes for second-line treatments may be mediated by the concomitant use of antihypertensive and lipid lowering drugs. For example, SGLT2is could be of greater benefit for patients with chronic heart failure (CHF) as they might augment the effects of diuretics in reducing the risks of CVD and End-Stage Renal Disease (ESRD). However, there is limited evidence about the synergistic effects of combining oral antidiabetic therapies with other drugs (polypharmacy).

To provide evidence-based personalised care, further research is therefore required to report relative effectiveness of second-line treatment according to individual patient's risk profiles. The risk profiles will use baseline measures drawing from the hypotheses about subgroup effects raised by the literature review, and advice from clinical experts and the PP representatives. The measures will include age, gender, ethnicity, established CVD, HbA1c, cholesterol levels, estimated glomerular filtration rate (eGFR), body mass index (BMI) and MLTC. Where the literature raises hypotheses about the relative effectiveness for subgroups of patients with particular risk factor combinations, for example that for patients with pre-existing CVD, the relative effectiveness of SGLT2 may be modified by the patients baseline renal function, we will consider the relative effectiveness according to combinations of baseline risk factors.

Why this research is needed now

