- a) By Clinical Commissioning Group in 2014 (n = 4,450 patients).
- *b)* By year across all Clinical Commissioning Groups (n = 61,787 patients).

Year intensifying treatment from metformin monotherapy

Patient-level covariates (see also outcomes)

For the one-year period *prior* to second-line treatment, we will extract information on patient characteristics (age, gender, ethnicity, index of multiple deprivation, marital status, approximate duration of diabetes), comorbidities (e.g. established CVD, CHF, CKD), and biomarker levels (HbA1c, high-density lipoprotein (HDL) cholesterol, low-density lipoprotein (LDL) cholesterol, total cholesterol, triglycerides, other systolic blood pressure (SBP), diastolic blood pressure (DBP), eGFR, body weight, and BMI). Each of these measures will be considered as part of the measurement of the baseline risk profile, and following the findings of the literature review and the design workshop, will be considered as variables for the subgroup analysis and in reporting results according to baseline risk profiles. The list of patient-level covariates

includes all those that will be required by the RAPIDS-UK model for predicting long-term effectiveness (see objective 5).

Treatment use

To address the research questions, the RAPIDS-UK model will require information on each patient's full longitudinal patterns of antidiabetic treatments, and those of concomitant medications for lipid lowering and anti-hypertensives. First, the model requires information on the drugs prescribed for the period *prior* to first-stage intensification. Second, the study requires data on the dates of prescription of second-line treatment, and those of lipid-lowering and antihypertensive medications *during* the period of second-line treatment. Third, for the period *after* clinicians have stopped prescribing second-line treatment, we require information on the prescription of subsequent anti-diabetic drugs and insulin, including newer alternatives such as Glucagon-like peptide-1s (GLP1s)

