For the main comparative effectiveness analysis (obj 2) we will handle all missing baseline and longitudinal outcome data by multiple imputation³² with chained equations.³³ This approach assumes data are missing at random. The imputation of each long36itudinal outcome at a given time point will use all relevant information, including measurements of the same outcome at other time points. This use of auxiliary information can help the study recover more accurate estimates of the unknown outcome values.³⁴ This will help ensure our study population is comparable across the second-line treatments at each time point. Partially observed covariates and outcomes^{35 36} will be multiple imputed by predictive mean matching with 10 donors, producing five imputed datasets. The number of imputations will be driven by the need to balance computational time with improved inference from increasing the number of imputations (see supplementary methods for further details). The imputation models developed for each covariate will be congenial with the form of outcome³⁷ (continuous or time to event). For the time-to-event endpoints, we will assume that there are no missing outcome data. All imputation models will be stratified by second line treatment (DPP-4 inhibitors, SGLT-2 inhibitors, sulfonylureas) and by whether the individual died or was censored before the relevant study end date.

[figure not shown]
Instrumental variable

Our proposed IV design follows research in pharmaco-epidemiology² that uses provider preference as an instrument for treatment prescribed. The IV will be the prescribing history in each CCG. This will be defined as the proportion of relevant prescriptions within the CCG for each first-stage treatment intensification in the last complete calendar year prior to the treatment intensification of the patient currently under consideration.

The key assumptions

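### Objective 2 imputes every incomplete covariate by predictive mean matching, with no exception for unordered categories such as ethnicity and marital status

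*Protocol*

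**What the plan says.** The rule is in Protocol section 4, under Missing data in the CPRD-HES linked cohort. For the objective 2 analysis, "we will handle all missing baseline and longitudinal outcome data by multiple imputation" using chained equations. The same paragraph then names the method: partially observed covariates and outcomes "will be multiple imputed by predictive mean matching with 10 donors", giving five completed datasets. No other imputation model is named for categorical variables.

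The same section gives the expected missingness. For baseline variables in general, "we expect <5% of patients will have missing values for baseline variables such as BMI". Ethnicity is singled out: "with the exception of ethnicity (c10%), for which missing data will be minimised by using HES admission data from linked episodes".

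The Patient-level covariates section lists "patient characteristics (age, gender, ethnicity, index of multiple deprivation, marital status, approximate duration of diabetes", so ethnicity and marital status are both planned covariates. It adds that each listed measure will be considered for subgroup analysis and for reporting by risk profile. The background section, in its account of the risk profiles, says "The measures will include age, gender, ethnicity, established CVD" and goes on to biomarkers and long-term conditions. Under Objective 2, Analysis, baseline covariates enter the first-stage treatment models.

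**The concern.** Predictive mean matching fits a linear regression to the incomplete variable, computes a predicted mean for everyone, and fills each gap with the observed value of someone whose predicted mean is close. This works well for HbA1c, BMI or blood pressure.

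For a variable with three or more unordered groups, the regression is on category codes. Their mean has no meaning and changes if the groups are renumbered. A single score also cannot in general separate several groups: a person predicted midway between codes 0 and 2 is matched to donors near code 1, whether or not group 1 resembles them. The imputed values are genuine categories and overall shares are roughly kept. What weakens is the link between a particular group and its predictors or its outcome.

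At stake are the quality of the adjustment for ethnicity in objective 2 and any objective 2 result reported by ethnicity. The study's aim is to personalise treatment, so such reporting is a natural use of the imputed data.

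**Working it through.** The protocol gives no figure to reproduce here. The check has three parts: scale, effect on group coefficients, and effect on drug contrasts.

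**Scale.** The Sample size calculation gives 6,000 + 13,000 + 6,700 = 25,700 patients. At 10% missing, 0.10 × 25,700 = 2,570 people need an imputed ethnicity. If hospital records cut this to 5% (an assumption; the remaining share is not stated), the number is 0.05 × 25,700 = 1,285.

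**Group coefficients.** This was a simulation in which every parameter is assumed and none comes from the protocol: 60 runs of 6,000 people; four unordered groups whose membership depends on age and deprivation; an outcome with true group effects of 1.5, −1.0 and 2.0 against the reference group and residual SD 4; and group missing at random given age and deprivation. Predictors for imputation were age, deprivation and the outcome. Matching used 10 donors, as in the protocol, on integer codes in two arbitrary orders. The comparison was multinomial logistic imputation. Loss = 1 − (imputed coefficient ÷ complete-data coefficient).

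About 10% missing:

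| Group | Complete data | Matching, order A | Matching, order B | Multinomial |
|---|---|---|---|---|
| 1 | 1.515 | 1.442 (4.8% lost) | 1.521 (none lost) | 1.530 |
| 2 | −1.038 | −0.789 (24.0% lost) | −0.787 (24.2% lost) | −1.044 |
| 3 | 2.008 | 1.836 (8.6% lost) | 1.892 (5.8% lost) | 2.030 |

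For group 2, for example, 1 − 0.789/1.038 = 24.0%. Group 2 suffers most because its effect has the opposite sign to the other two, and a score linear in the outcome cannot pick it out. Multinomial imputation is within about 1% of complete data for all three groups.

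Group shares among those imputed moved little: true 0.663/0.195/0.102/0.040, against 0.652/0.209/0.095/0.044 under order A. At about 30% missing, well above the protocol's expectation, the losses were 15.9%, 59.7% and 23.8% (order A) and 1.4%, 64.5% and 15.0% (order B). Multinomial imputation gave 1.505, −1.016 and 2.020.

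**Drug contrasts.** A separate simulation, again with assumed inputs, used 25,700 people, three drugs and five ethnic groups affecting both drug and outcome. Matching was done within drug, and adjustment was by ordinary least squares rather than two-stage residual inclusion. At 10% missing the contrasts moved by at most 0.024 mmol/mol, against a sampling SD of about 0.17 to 0.18; 0.024/0.17 = 0.14 of an SD. With the codes reordered the shift was 0.0002. At 5% missing it was at most 0.014. Ethnicity coefficients in this simulation were diluted by up to about 11% at 10% missing in one code order.

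**The case against.** The best reply is that the rule is written for objective 2, which reports drug contrasts, and these barely move. Effect modification is planned by age, baseline HbA1c and long-term conditions (Objective 4), and the Sample size calculation gives CVD, age, HbA1c and eGFR as example subgroups. Ethnicity is only a candidate, named in the background and left open in Patient-level covariates. All of this stands, and it sets the size of the point.

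Missingness may also be below 10%. The Overall population section excludes patients without hospital linkage, so everyone included can contribute hospital records. If the 10% is the level before that step, which the text leaves open, the effect shrinks accordingly. A complete-records sensitivity analysis is planned and gives a partial check.

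One could also say that the model for each variable belongs in a supplement or analysis plan. That is weaker. The pointer to supplementary methods is attached to the number of imputations, and the remark on congeniality concerns whether the analysed outcome is a continuous measure or a survival time. Neither exempts categorical covariates from a method that the text states. The supplement is not at hand and may name other models; if so, the protocol sentence should say so.

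A reader might infer four stronger things, which the documents do not support:

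- That the primary result is biased to a degree that matters. The check above shows otherwise under its assumptions.
- That the disparities analysis of objective 1, where ethnicity is the exposure, is compromised. The protocol does not say whether the rule extends to it.
- That ethnicity has the most missing data of any variable. This holds only among baseline covariates with a stated figure, since missingness of follow-up outcomes is not given.
- That nearly half of the distinction between minority groups is lost. One simulation with assumed inputs did show a gap falling from 1.43 to 0.77 SD (46%), but only among imputed people. At 9.6% missing that is 0.46 × 9.6% = 4.4% over the cohort.

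**Conclusion.** The point holds as a minor one. For objective 2 the protocol fixes a method that does not suit unordered covariates with more than two groups and applies it to ethnicity, which has the highest stated missing share at baseline. At about 10% missing, group coefficients may be diluted by anything from almost nothing to about a quarter, depending on group and code order. The effect on overall drug contrasts should be negligible.

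These sizes rest on assumed group shares, effects and missingness mechanisms, and on integer scoring of categories, since the protocol names neither the software nor the scoring. The drug-contrast check used ordinary least squares and not the planned estimator. The direction is more secure than the size: the separate simulations agree that matching on codes weakens group-specific associations. Missing shares for marital status are not stated separately, so no size is given for it.

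**What to change.** Amend the missing-data paragraph so that predictive mean matching applies to continuous variables only (HbA1c, BMI, blood pressure, lipids, eGFR), and state that ethnicity and marital status are imputed by multinomial logistic regression within the same chained equations. Logistic regression for binary covariates is optional, because the code-order problem does not arise with two categories. State also whether the rule covers objective 1.

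The cost is one setting per variable in the imputation software and slightly longer run time. Because imputation is stratified by drug and by death or censoring, some ethnic groups may be too sparse within a stratum for a multinomial model and may need merging there. Any merging should be specified in advance.
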